3.1.5 Management of Study Medication Related Toxicities

Based on the mechanism of action of MEDI4736 and tremelimumab leading to T-cell activation and proliferation, there is the possibility of observing irAEs during the conduct of this study. Potential irAEs may be similar to those seen with the use of ipilimumab, nivolumab, and BMS-936559 and may include immune-mediated enterocolitis, dermatitis,

[figure not shown]
hepatitis, and endocrinopathies ([Hodi et al, 2010](#); [Brahmer et al, 2012](#); [Topalian et al 2012](#); [Wolchok et al, 2013](#)). Subjects should be monitored for signs and symptoms of irAEs. In the absence of an alternate etiology (eg, infection or PD), an immune-related etiology should be considered for signs or symptoms of enterocolitis, dermatitis, hepatitis, and endocrinopathy. In addition to the dose modifications shown in [Appendix 5](#), it is recommended that management of irAEs follow the guidelines outlined for ipilimumab ([Weber J et al, 2012](#)).

If the investigator has any question in regards to an AE being an irAE, the investigator should immediately contact the medical monitor. Dose modifications may be required for AEs that are clearly not attributed to MEDI4736 or tremelimumab (such as an accident) or for laboratory abnormalities that are deemed asymptomatic, require no intervention, and are documented in the medical records. Laboratory abnormalities that are felt to meet these criteria must be discussed and agreed on by the medical monitor before treatment can be continued. Dose reductions of MEDI4736 and tremelimumab are not permitted.

Dose interruptions of MEDI4736 and tremelimumab may be required in the event of treatment-related toxicity. General guidelines regarding dose modifications are provided in [Appendix 5](#). In addition, management guidelines for AESIs are detailed in [Section 5.3](#). All toxicities will be graded according to NCI CTCAE v4.03. In case of doubt the investigator should consult with the medical monitor.

3.2.2 Rationale for Study Population

The proposed study population, comprising adult subjects with metastatic or recurrent gastric or GEJ adenocarcinoma that have progressed during or after 1 or 2 prior standard regimens for recurrent or metastatic disease, represents a high unmet medical need. This tumor indication, described below, presents an opportunity for novel treatment approaches that may lead to improved clinical outcomes.

In 2014, it is estimated that 22,220 and 18,170 people will be newly diagnosed with gastric cancer and esophageal cancer, respectively, whereas 26,440 individuals will die due to upper GI tumors ([Siegel et al, 2014](#)). Gastroesophageal cancer remains endemic in many parts of the world, with an estimated new cancer incidence of 1,471,000 people or 11.6% of the global cancer burden and an annual death rate of 1,144,000 people or 15.1% of cancer-related deaths worldwide ([Ferlay et al, 2010](#)). Globally, gastric cancer is the second leading cause of cancer-related mortality ([Luis et al, 2013](#)).

Current therapeutic strategies for advanced gastric or GEJ adenocarcinoma are limited, and survival rarely exceeds 1 year despite aggressive treatment with chemotherapy. A number of different drugs (eg, alkylating agents, platinum compounds, 5-fluorouracil [5-FU], and taxanes) are available for the treatment of gastroesophageal cancer, but no means of selecting therapy based on the tumor biology is currently available. At present, the combination of a

platinum and fluorouracil agent either alone or in combination with a third drug such as epirubicin or taxane constitutes the most effective treatment option in the first-line metastatic setting ([Cunningham et al, 2008](#)). Standard first-line options include docetaxel, cisplatin, and 5-FU; epirubicin, cisplatin, and capecitabine/epirubicin, oxaliplatin, and capecitabine; or folinic acid, 5-FU, and oxaliplatin.

The vascular endothelial growth factor receptor 2 antagonist, ramucirumab, as evaluated in the REGARD study and recently approved by the US FDA, has demonstrated modest activity in subjects with advanced gastric or GEJ adenocarcinoma who progressed after first-line platinum- or fluoropyrimidine-containing chemotherapy ([Fuchs et al, 2014](#)). Median OS was 5.2 months in the ramucirumab group versus 3.8 months in the placebo group (HR 0.776, 95% confidence interval [CI], 0.603-0.998; $p = 0.047$). In the RAINBOW study, more than 600 subjects with metastatic gastric or GEJ adenocarcinoma who had disease progression on or within 4 months after first-line platinum- and fluoropyrimidine-based combination therapy were randomized to paclitaxel plus ramucirumab or paclitaxel alone ([Wilke et al, 2014](#)). Median OS was 9.63 months and 7.36 months, respectively (HR 0.807; 95% CI, 0.678-0.962; $p = 0.017$), and median PFS was 4.40 and 2.86 months, respectively (HR 0.635; 95% CI, 0.536-0.752; $p < 0.0001$). Median time to progression was 5.5 months with ramucirumab plus paclitaxel versus 3.0 months with paclitaxel alone ($p < 0.0001$), and ORR was 28% versus 16%, respectively ($p = 0.0001$). Based on these results, the combination of ramucirumab plus paclitaxel is expected to become the standard of care in the second-line setting for metastatic upper GI tumors.

Additional FDA-approved second-line agents include docetaxel and irinotecan. In the COUGAR-02 study, median OS was 5.2 months with docetaxel compared with 3.6 months with best supportive care (BSC; HR 0.67; 95% CI, 0.49–0.92; $p = 0.01$; [Ford et al, 2014](#)). Kang and colleagues evaluated chemotherapy (docetaxel 60 mg/m² every 3 weeks or irinotecan 150 mg/m² Q2W) plus BSC versus BSC alone in subjects with advanced gastric cancer who received 1 or 2 prior fluoropyrimidine- and platinum-based chemotherapy regimens ([Kang et al, 2012](#)). The median OS was 5.3 months with chemotherapy plus BSC ($n = 133$) versus 3.8 months with BSC alone ($n = 69$; HR 0.657; 95% CI, 0.485-0.891; $p = 0.007$). There was no median OS difference between docetaxel and irinotecan (5.2 versus 6.5 months, respectively; $p = 0.116$). Despite these advances, the toxicity profile of second-line agents is poor and survival is still between 6 to 9 months. Consequently, immunotherapies hold potential promise in this setting.

To date, a number of Asian studies have investigated PD-L1 expression in gastric cancer. Zheng and colleagues evaluated 80 advanced gastric cancer subjects and 40 healthy controls.

They reported significant upregulation of PD-L1 in advanced gastric cancer patients compared with healthy people ($p = 0.006$; [Zheng et al, 2014](#)). The expression of PD-L1 was significantly correlated with differentiation ($p = 0.026$) and lymph node metastasis ($p = 0.041$). Wu and colleagues examined PD-L1 expression in cases of human gastric carcinoma ($n = 102$), adenoma ($n = 10$), and normal tissues ($n = 10$; [Wu et al, 2006](#)). Programmed cell death ligand 1 was not detected in normal gastric tissues, and very weak immunodetection in gastric adenomas, but PD-L1 was detected in 42.2% of gastric carcinoma tissues. There was no correlation between PD-L1 immunolocalization and patient age, sex, tumor location, or the degree of tumor differentiation in gastric carcinomas. However, PD-L1 immunodetection was significantly correlated with tumor size, invasion, lymph node metastasis, and survival time. Multivariate analysis demonstrated that PD-L1 immunodetection could be used as an independent factor to evaluate the prognosis of gastric carcinoma.

3.2.3 Rationale for Endpoints

Safety

Standard safety parameters (AEs, SAEs, laboratory evaluations, vital signs, ECGs, and physical examinations) will be employed to assess the safety profile of MEDI4736 in combination with tremelimumab, MEDI4736 monotherapy, and tremelimumab monotherapy.

Primary and Secondary Efficacy Assessments

OR and DC as assessed by RECIST v1.1 ([Eisenhauer et al, 2009](#)) per blinded central review, are standard measures of clinical activity. OS is considered the “gold standard” for quantifying clinical benefit, with PFS being an acceptable surrogate. In the Phase 2 portion of the study, blinded central review will be performed to confirm response data.

Tumoral IFN- γ Gene Expression Signature

[figure not shown]
Clinical trials and preclinical studies have demonstrated the predictive nature of an elevated Th1 gene signature within the tumor and the subsequent response to immunotherapy for solid tumors ([Ulloa-Montoya et al, 2013](#); [Peng et al, 2015](#)). IFN- γ is one of the hallmark cytokines, both initiating and propagating the Th1 response. Its expression is closely tied to other proteins and cytokines within the tumor microenvironment. Based on internal investigations, an IFN- γ gene expression panel was identified consisting of 4 genes that will be utilized to try and identify a unique population of gastric or GEJ adenocarcinoma subjects who may benefit from treatment with immune checkpoint inhibitors and to identify correlations between IFN- γ gene expression and clinical activity of MEDI4736 in combination with

tremelimumab. IFN- γ gene expression testing will be performed for all Phase 2 treatment cohorts; retrospective testing will be performed as necessary.

PD-L1 Expression

In Study CD-ON-MEDI4736-1108, as of 21Aug2014, the DCR at 12 weeks (DCR-12w) was 33% (115/352 subjects) and ORR was 10% (36/352 subjects) in subjects (across 8 tumor types) treated with MEDI4736 10 mg/kg Q2W ([Segal et al, 2014](#)). Greater DCR-12w (47% vs 28%) and ORR (22% vs 5%) were observed in PD-L1-positive versus PD-L1-negative subjects, based on a proprietary IHC assay which detects PD-L1 staining on tumor cells.

Of the 41 subjects with gastroesophageal cancer who have been dosed in Study CD-ON-MEDI4736-1108, 28 were evaluable for efficacy analysis ([Segal et al, 2014](#)). In these subjects, DCR-12w was 25% (7/28 subjects).

Collection of Subject Selection Biomarker Data

Candidate biomarkers for subject selection will be assessed to determine whether these markers predict which subjects are most likely to respond to treatment with MEDI4736 in combination with tremelimumab, MEDI4736 monotherapy, or tremelimumab monotherapy.

4 MATERIALS AND METHODS

4.1 Subjects

4.1.1 Number of Subjects

Up to approximately 135 subjects in Phase 1b/2 will be enrolled at up to approximately 40 study centers globally. Additional subjects may be enrolled if dose de-escalation is required or intermediate dose levels are explored.

4.1.2 Inclusion Criteria

Subjects must meet all of the following criteria:

1. Male or female subjects; age \geq 18 years at the time of screening or age of consent according to local law.
2. Written informed consent and any locally required authorization, Health Insurance and Portability and Accountability Act in the US, European Union (EU) Data Privacy Directive in the EU obtained from the subject/legal representative prior to performing any protocol-related procedures, including screening evaluations.
3. ECOG performance status of 0 or 1.
4. Histologically or cytologically confirmed metastatic or recurrent gastric or GEJ adenocarcinomas. Note: GEJ adenocarcinomas are defined as tumors that have their center within 5 cm proximal and distal of the anatomical cardia, as described in the Siewert classification system ([Siewert et al, 2000](#)).
5. Prior lines of therapy:
 - a. For Phase 1b: Must have received and have progressed, or are refractory to one systemic platinum- or fluoropyrimidine-based chemotherapy regimen for metastatic or recurrent disease.
 - b. For Arms A, B, and C of Phase 2: Must have received and have progressed, or are refractory to one systemic platinum- or fluoropyrimidine-based chemotherapy regimen for metastatic or recurrent disease, or
Must have received and have progressed, or are refractory to one systemic platinum or fluoropyrimidine-based therapy as part of neoadjuvant or adjuvant regimen with relapse within 6 months of therapy.
 - c. For Arm D of Phase 2: Must have received and have progressed, or are refractory to two systemic regimens (one standard platinum- or fluoropyrimidine-based chemotherapy regimen and one approved regimen) for metastatic or recurrent disease.

d. For Arm E of Phase 2: Subjects with a positive IFN- γ gene expression signature (as defined in Section 4.3.8.1) must have received and have progressed, or are refractory to one systemic platinum- or fluoropyrimidine-based chemotherapy regimen for metastatic or recurrent disease, or

Must have received and have progressed, or are refractory to one systemic platinum- or fluoropyrimidine-based therapy as part of neoadjuvant or adjuvant regimen with relapse within 6 months of therapy, or

Must have received and have progressed, or are refractory to two systemic regimens (one standard platinum- or fluoropyrimidine-based chemotherapy regimen and one approved regimen for metastatic or recurrent disease).

e. Subjects who have received and have progressed, or are refractory to one systemic platinum- or fluoropyrimidine-based therapy as part of neoadjuvant or adjuvant regimen with relapse within 6 months will count as a line of therapy in the metastatic/recurrent setting.

6. Screening for IFN- γ expression prior to Arm E enrollment:

- Subjects who are being considered for enrollment on Arm E may undergo pre-screening for IFN- γ gene expression either at the time of disease progression or after having completed a minimum of 60 days of the prior line of systemic therapy. In addition, they should meet all other eligibility criteria for enrollment, with the exception of prior lines of therapy if they are being screened during first-or second-line treatment.
- Subjects enrolling to Arm E must consent to provide archival tumor tissue for IFN- γ testing. Only subjects with a positive IFN- γ gene expression signature (as defined in Section 4.3.8.1) will be eligible for enrollment to Arm E. IFN- γ testing must be completed to determine enrollment eligibility prior to initiation of therapy. If eligible, subjects must consent to initial and subsequent tumor biopsy samples, if possible.

7. Subjects must have at least one measurable lesion according to RECIST v1.1.

- A previously irradiated lesion can be considered a target lesion if the lesion is well defined, measurable and there is objective evidence of interval increase in size.

8. Subjects must have at least one lesion amenable to biopsy and must consent to and provide both pre-treatment and on-treatment tumor biopsies for Phase 2 (optional for Phase 1b). Fresh tumor biopsies should be preferentially obtained from tumor tissues that are safely accessible as determined by the investigator and achieved via non-significant risk procedures (refer to Section 4.3.2.1). Tumor lesions used for biopsy should not be lesions used as RECIST target lesions. Sites are encouraged to confirm adequacy of tumor biopsy material at the time of the procedure.

9. Subjects must consent to provide archival tumor tissue (initial and subsequent tumor biopsy samples, if possible) for correlative biomarker studies (for both Phase 1b and 2), if available. Availability of tissue for transfer to sponsor should be confirmed prior to initiation of study therapy.

10. Adequate organ and marrow function, as defined below. Criteria "a," "b," and "c" cannot be met with ongoing or recent blood transfusions (within 14 days of starting first dose) or require growth factor support (within 28 days of starting the first dose)

- Hemoglobin \geq 8 g/dL

- b. Absolute neutrophil count $\geq 1,500/\mu\text{L}$
- c. Platelet count $\geq 100,000/\mu\text{L}$
- d. Total bilirubin $\leq 1.5 \times \text{ULN}$ except subjects with documented Gilbert's syndrome ($> 3 \times \text{ULN}$)
- e. ALT and AST $\leq 3 \times \text{ULN}$
- f. Calculated creatinine clearance $\geq 50 \text{ mL/minute}$ as determined by Cockcroft-Gault (using actual body weight) or 24-hour urine creatinine clearance

11. Female patients of child-bearing potential: Female subjects of childbearing potential who are sexually active with a non-sterilized male partner must use at least one **highly** effective method of contraception ([Table 4.1.2-1](#)) from the time of screening, and must agree to continue using such precautions for 180 days after the last dose of MEDI4736 + tremelimumab combination therapy or 90 days after the last dose of MEDI4736 monotherapy. Non-sterilised male partners of a female subject must use male condom plus spermicide throughout this period. Cessation of birth control after this point should be discussed with a responsible physician. Not engaging in sexual activity for the total duration of the drug treatment and the drug washout period is an acceptable practice; however, periodic abstinence, the rhythm method, and the withdrawal method are not acceptable methods of contraception. Female subjects should refrain from breastfeeding throughout this period.

- a. Females of childbearing potential are defined as those who are not surgically sterile (ie, bilateral tubal ligation, bilateral oophorectomy, or complete hysterectomy) or post-menopausal
Women will be considered post-menopausal if they have been amenorrheic for 12 months without an alternative medical cause. The following age-specific requirements apply:
 - i. Women < 50 years of age would be considered post-menopausal if they have been amenorrheic for 12 months or more following cessation of exogenous hormonal treatments and if they have luteinizing hormone and follicle-stimulating hormone levels in the post-menopausal range for the institution or underwent surgical sterilization (bilateral oophorectomy or hysterectomy).
 - ii. Women ≥ 50 years of age would be considered post-menopausal if they have been amenorrheic for 12 months or more following cessation of all exogenous hormonal treatments, had radiation-induced menopause with last menses > 1 year ago, had chemotherapy-induced menopause with last menses > 1 year ago, or underwent surgical sterilization (bilateral oophorectomy, bilateral salpingectomy or hysterectomy).
- b. Highly effective methods of contraception, defined as one that results in a low failure rate (ie, less than 1% per year) when used consistently and correctly are described in [Table 4.1.2-1](#). Note that some contraception methods are not considered highly effective (eg, male or female condom with or without spermicide; female cap, diaphragm, or sponge with or without spermicide; non-copper containing intrauterine device; progestogen-only oral hormonal contraceptive pills where inhibition of ovulation is not the primary mode of action [excluding Cerazette/desogestrel which is considered highly effective]; and triphasic combined oral contraceptive pills).

12. Male patients with a female partner of childbearing potential

- a. Non-sterilized male subjects who are sexually active with a female partner of childbearing potential must use male condom plus spermicide from screening through 180 days after receipt of the final dose of MEDI4736 + tremelimumab combination therapy or 90 days after receipt of the final dose of MEDI4736 monotherapy. Not engaging in sexual activity is an acceptable practice; however, occasional abstinence, the rhythm method, and the withdrawal method are not acceptable methods of contraception. Male subjects should refrain from sperm donation throughout this period.
- b. Female partners (of childbearing potential) of a male subject must use a highly effective method of contraception throughout this period ([Table 4.1.2-1](#)).

Table 4.1.2-1 Highly Effective^a Methods of Contraception (< 1% failure rate)

Barrier Methods	Hormonal Methods

• Copper T intrauterine device• Levonorgestrel-releasing intrauterine system (eg, Mirena[®])^a	
• Implants: Etonogestrel implants: eg, Implanon[®] or Norplan[®]• Intravaginal device: eg ethinylestradiol / etonogestrel-releasing intravaginal devices: eg, NuvaRing[®]• Injection: Medroxyprogesterone injection: eg, Depo-Provera[®]• Combined Pill: Normal and low dose combined oral contraceptive pill• Patch: Norelgestromin/ethinylestradiol-releasing transdermal system: eg, Ortho Evra[®]• Minipill: Progesterone based oral contraceptive pill using desogestrel: Cerazette[®] is currently the only highly effective progesterone based pill

^a This is also considered a hormonal method.

13. All patients: Patients should not donate blood or blood components while participating in this study and through 180 days after receipt of the final dose of MEDI4736 + tremelimumab combination therapy or 90 days after receipt of the final dose of MEDI4736 or tremelimumab.

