3.1.3.2 Dose-limiting Toxicity

Dose-limiting toxicity will be evaluated during the DLT evaluation period in Phase 1b.

Subjects who do not remain on the study up to this time for reasons other than DLT will be replaced with another subject at the same dose level. Dose-limiting toxicity will be graded according to the National Cancer Institute Common Terminology Criteria for Adverse Events (NCI CTCAE) v4.03.

A DLT will be defined as any Grade 3 or higher toxicity that occurs during the DLT evaluation period. Toxicity that is clearly and directly related to the primary disease or to another etiology is excluded from this definition. The following will be DLTs:

- Any Grade 4 irAE
- Any \geq Grade 3 colitis
- Any Grade 3 or 4 noninfectious pneumonitis irrespective of duration
- Any Grade 2 pneumonitis that does not resolve to \leq Grade 1 within 3 days of the initiation of maximal supportive care
- Any Grade 3 irAE, excluding colitis or pneumonitis, that does not downgrade to Grade 2 within 3 days after onset of the event despite optimal medical management including systemic corticosteroids or does not downgrade to \leq Grade 1 or baseline within 14 days
- Liver transaminase elevation $> 8 \times$ ULN or total bilirubin $> 5 \times$ ULN
- Any \geq Grade 3 non-irAE, except for the exclusions listed below

The definition excludes the following conditions:

- Grade 3 fatigue lasting \leq 7 days
- Grade 3 endocrine disorder (thyroid, pituitary, and/or adrenal insufficiency) that is managed with or without systemic corticosteroid therapy and/or hormone replacement therapy and the subject is asymptomatic
- Grade 3 inflammatory reaction attributed to a local antitumor response (eg, inflammatory reaction at sites of metastatic disease, lymph nodes, etc)

- Concurrent vitiligo or alopecia of any AE grade
- Grade 3 infusion-related reaction (first occurrence and in the absence of steroid prophylaxis) that resolves within 6 hours with appropriate clinical management
- Grade 3 or 4 neutropenia that is not associated with fever or systemic infection that improves by at least 1 grade within 3 days. Grade 3 or Grade 4 febrile neutropenia will be a DLT regardless of duration or reversibility
- Grade 3 or 4 lymphopenia
- Grade 3 thrombocytopenia that is not associated with clinically significant bleeding that requires medical intervention, and improves by at least 1 grade within 3 days

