17. Other invasive malignancy within 2 years except for noninvasive malignancies such as cervical carcinoma in situ, in situ prostate cancer, non-melanomatous carcinoma of the skin, ductal carcinoma in situ of the breast that has been surgically cured.
18. Uncontrolled intercurrent illness including, but not limited to, ongoing or active infection, symptomatic congestive heart failure, uncontrolled hypertension, unstable angina pectoris, cardiac arrhythmia, active peptic ulcer disease or gastritis, or psychiatric illness/social situations that would limit compliance with study requirement, substantially increase risk of incurring AEs from MEDI4736 or tremelimumab, or compromise the ability of the subject to give written informed consent.
19. Any condition that, in the opinion of the investigator or sponsor, would interfere with evaluation of the investigational products or interpretation of subject safety or study results.
20. Subjects who are involuntarily incarcerated or are unable to willingly provide consent or are unable to comply with the protocol procedures.

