4.1.4 Subject Enrollment and Randomization

Study participation begins (ie, a subject is “enrolled”) once written informed consent is obtained. Once informed consent is obtained, a subject identification (SID) number will be assigned by a central system (eg, an interactive response system [IXRS]), and the pre-screening/screening evaluations may begin to assess study eligibility

(inclusion/exclusion) criteria. The SID number will be used to identify the subject during the pre-screening/screening process and throughout study participation.

A master log of all consented subjects will be maintained at the site and will document all screening failures (ie, subjects who are consented but do not meet study eligibility criteria), including the reason(s) for screening failure.

Subjects who fail to meet the inclusion/exclusion criteria (ie, screening failures) should not receive investigational products. There can be no exceptions to this rule. Subjects who are screening failures should be withdrawn from the study.

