PD-L1 expression is around 40%, approximately 18 evaluable subjects with high PD-L1 expression for either arms A or B will be expected. The probability of observing at least 1 responder out of 18 evaluable subjects will be at least 90% if the response rate is at least 15%. Additional subjects with high PD-L1 expression may be enrolled in order to further evaluate this population.

With approximately 45 evaluable subjects for Arm A and 22 evaluable subjects for Arm C, the study has 85% power to detect a difference of 35% vs 10% in the response (or PFS-6) rates assuming a 1-sided $\alpha = 0.10$ between the combination arm and the tremelimumab monotherapy arm.

Arm D

It is planned to enroll 25 subjects in Arm D.

Arm E (as of Protocol Amendment 6)

Approximately 40 additional subjects who are biomarker positive will be assigned to Arm E. Assuming 10% of the subjects are not evaluable for response or drop-out without PFS event before 6 months, approximately 36 evaluable subjects for Arm E are expected. The sample size determination is based primarily on the consideration of providing the estimation with reasonable precision. As shown in Table 2.4.2-2, when the ORR is expected to be in the 28% to 39% range, a total of 36 subjects would provide a width of 12% to 14% between the observed point estimator and its lower limit of the exact 90% CI. If 19 of 36 subjects have PFS \geq 6 months, the PFS-6 will have an estimate of 53% with a 90% CI of (39%, 67%). Assuming that PFS follows an exponential distribution, the PFS-6 of 53% will correspond to a median PFS of 6.6 months, which is a 50% increase from the 4.4 months observed for ramucirumab plus paclitaxel in subjects with metastatic gastric or GEJ adenocarcinoma following disease progression on first-line platinum- and fluoropyrimidine-based combination therapy in the RAINBOW study.

Table 2.4.2-2 Observed ORR/PFS-6 with 90% CI (Arm E)

N	Number of Subjects with OR	ORR	2-sided Exact 90% CI	
36	10	28%	16%	43%
36	14	39%	25%	54%

N	Number of Subjects with PFS at 6 Months	PFS6	2-sided 90% CI	
36	19	53%	39%	67%

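### Inclusion criterion 10d writes its Gilbert's syndrome bilirubin exception as a floor (> 3 x ULN) where a ceiling is evidently meant

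*Protocol*

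**What the plan says.** Protocol 4.1.2 opens its list with "Subjects must meet all of the following criteria", so each item is mandatory. Criterion 10 is headed "Adequate organ and marrow function, as defined below". Item d reads "Total bilirubin $\leq 1.5 \times \text{ULN}$ except subjects with documented Gilbert's syndrome", followed by a bracket containing > 3 x ULN; the exception itself is printed as "except subjects with documented Gilbert's syndrome ($> 3" x ULN). The next item, 10e, sets ALT and AST at no more than 3 x ULN, written as a ceiling.

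Protocol 4.1.4 says that subjects who fail the inclusion or exclusion criteria "should not receive investigational products. There can be no exceptions to this rule".

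Neither the synopsis nor the exclusion criteria give a bilirubin limit, and the amendment summaries in Protocol section 9 mention no change to one. The SAP does not restate the criterion.

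**The concern.** The heading of criterion 10 asks for adequate organ function, and item d serves it with an upper bound. A relaxation for Gilbert's syndrome should raise that bound. As printed, it admits only values above 3 x ULN and sets no limit above that. A subject with mildly raised bilirubin is turned away, while one with a much higher value qualifies.

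Two things are at stake:

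- **Consistency across sites.** A site that follows the words and a site that follows the likely intent decide in opposite directions. The second also records what looks like an eligibility deviation.
- **Interpretable liver safety data.** Protocol 3.1.3.2 lists "ULN or total bilirubin $> 5" x ULN as dose-limiting, and Protocol 4.1.6 (items 4 and 5) stops investigational product for an AE meeting DLT criteria. Protocol 5.6.2 uses bilirubin above 2 x ULN, together with ALT or AST above 3 x ULN, as its hepatic reporting trigger. A subject admitted under the literal rule starts above the bilirubin part of that trigger and may start above the DLT level.

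**Working it through.** The plan gives no figure to reproduce. The check is of the inequalities.

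**Inputs**

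- General cap: total bilirubin <= 1.5 x ULN (Protocol 4.1.2, 10d).
- Exception for documented Gilbert's syndrome: > 3 x ULN, no upper limit (same item).
- DLT level: total bilirubin > 5 x ULN (Protocol 3.1.3.2).
- Arm E size: "Approximately 40 additional subjects who are biomarker positive will be assigned to Arm E" (SAP 2.4.2, Arm E).

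**Eligible sets.** Let B be total bilirubin in multiples of ULN for a subject with documented Gilbert's syndrome.

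- Floor (literal): eligible if B <= 1.5 or B > 3.
- Ceiling (likely intent): eligible if B <= 3.
- Full exemption (bracket taken as mere description): eligible at any B.

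| B (x ULN) | Floor | Ceiling | Full exemption |
|---|---|---|---|
| <= 1.5 | eligible | eligible | eligible |
| > 1.5 to 3, e.g. 2 | not eligible | eligible | eligible |
| > 3, e.g. 6 | eligible | not eligible | eligible |

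The floor and ceiling readings agree only for B <= 1.5 and conflict at every higher value. The full exemption sides with the ceiling from 1.5 to 3 and with the floor above 3. All three agree in no band above 1.5. The literal entrant at B = 6 is already above the DLT level of 5.

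**Other text that might settle it.** Exclusion 19 (Protocol 4.1.3) covers "Any condition that, in the opinion of the investigator or sponsor, would interfere with evaluation of the investigational products". It gives discretion but no number. It could keep out a subject at 6 x ULN. It cannot make a subject at 2 x ULN eligible under the floor reading, because that subject has failed a mandatory inclusion criterion.

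**Number affected.** Protocol 3.1.1 reports Phase 1b and Arm D complete and enrolment to Arms A, B and C stopped, which leaves Arm E. The documents give no frequency of Gilbert's syndrome. With an assumed 2% to 10%:

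- 40 x 0.02 = 0.8 subjects
- 40 x 0.10 = 4 subjects

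These are upper figures, since subjects with B <= 1.5 are unaffected. That fraction is not known.

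**The case against.** The strongest objection is that everything rests on one symbol in text that a program read from PDF, and that the extraction is visibly faulty elsewhere. For example, the formulas in SAP 3.4.1 use two different symbols for the same survival estimate, and the list label for hemoglobin in criterion 10 is missing. A misread sign is therefore possible, and this part of the objection stands as a caveat. Against it, the sentence is complete and unredacted, and the other inequalities in criterion 10 (hemoglobin, neutrophils, platelets, transaminases, creatinine clearance, and the 1.5 x ULN cap on the same line) all point the way they should. That favours a drafting slip but does not prove it.

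Second, the intent is fairly obvious, and a site that noticed the conflict with the heading would probably query it. That is likely, and it is why the point is minor. It does not make the printed rule right, and nothing in the documents tells sites which reading to use.

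Third, other safeguards exist: the transaminase limit in 10e, exclusions 18 and 19, on-study liver tests, and the interruption rules in Protocol 5.6.2. In addition, the DLT definition leaves out toxicity clearly due to another etiology, which might cover raised bilirubin from Gilbert's syndrome. These reduce the risk of harm. None sets a bilirubin ceiling for these subjects or admits the subject at 2 x ULN.

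Finally, the number affected may be zero, and SAP versions 2.1 and 3.0 (April and May 2019) already refer to preparing the clinical study report, so Arm E enrolment may have ended. Both points are fair and limit the practical gain from an amendment.

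**Conclusion.** The concern holds on the text as supplied: criterion 10d is wrong as written for subjects with documented Gilbert's syndrome and bilirubin above 1.5 x ULN, and no other provision corrects it. It is a minor error in an operative eligibility rule. It plausibly touches no more than about 4 of roughly 40 Arm E subjects, and possibly none; that range rests on the assumed 2% to 10% frequency. Sample size, power, alpha, endpoints and analysis populations do not change. Confidence is medium, because the conclusion depends on the sign being the same in the source document. That 3 x ULN was meant as the ceiling is an inference from the number already in the criterion, not something the documents state.

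**What to change.** First check the sign in the source document. If it is as shown, reword 10d so that total bilirubin must be <= 1.5 x ULN, or <= 3 x ULN for subjects with documented Gilbert's syndrome, with the sponsor confirming the 3 x ULN value. This closes the gap between 1.5 and 3 x ULN and bars anything higher. The cost is one symbol or phrase in the next amendment or a clarification letter to sites. If Arm E enrolment has already finished, check instead whether any enrolled or screen-failed subject had Gilbert's syndrome with bilirubin above 1.5 x ULN, and note how the criterion was applied.
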